8.4 Concurrent Medications and Non-Drug Therapies

Subjects in both groups will receive the site's SOC, which may include medication and/or non-drug therapies. However, subjects in both groups should not perform any rehabilitation activities that may conflict with the device Instructions for Use [REDACTED] during the study before and up to 4 weeks after the TKA. In addition, subjects in both groups will not be

allowed to use other electrical stimulation therapies [REDACTED] before and up to 4 weeks after their TKA. All interventions targeting pain control will be recorded on the appropriate pages of the CRF.

8.5 Study Plan

The study includes 11 Visits. Appendix A provides schedules of the study procedures for both groups.

8.5.1 Visit 1: Consent and Randomization

Subjects will receive a detailed explanation of study-specific procedures as well as the risks and benefits of participating in the study. The subject will be asked to sign the approved study consent during this visit. If the subject agrees to participate by signing the consent form, all inclusion/exclusion criteria will be verified by completing the eligibility form and then all baseline information and outcome measurements will be collected and recorded on the appropriate case report form (CRF) in accordance with the schedule of study procedures (see Appendix A).

Subjects will receive a one-week daily diary to be completed prior to Visit 2.

8.5.2 Visit 2: Lead Placement Visit (Group #1 only) and Check-in Call (Both Groups)

[REDACTED]

[REDACTED]

[REDACTED]

[REDACTED]

[REDACTED]

[REDACTED]

[REDACTED]

[REDACTED] [REDACTED]

[REDACTED] [REDACTED]

[REDACTED]

[REDACTED]

[REDACTED]

[REDACTED]

[REDACTED]

[REDACTED]

[REDACTED]

[REDACTED]

[REDACTED]
[REDACTED]
At the conclusion of the Lead Placement Visit, subjects in Group #1 will either:

a. Proceed to treatment phase:

(i) Subjects with acceptable lead placement and stimulation parameters will be prepared to proceed to the treatment phase (See Below). These subjects will start completing a daily diary.

OR

b. Return for another Visit 2:

(i) If there is not sufficient time to complete lead placement or the testing, or if the subject does not respond to stimulation, the investigator may present the subject with the option to return for a repeat lead placement visit.
[REDACTED]

OR

c. Terminate from the Study:

[figure not shown]
(i) If the subject does not wish to continue with further lead placement or if an additional lead placement visit is needed [REDACTED], they will be terminated from the study if no adverse events (AE) are noted at the 24-48 hour telephone Check-In Call. If an AE is noted, the subject will be followed until the AE resolves.

Treatment Phase:

[REDACTED]

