2.0 Protocol Synopsis

Title	A Prospective, Comparative Effectiveness Randomized Controlled Trial of SPR peripheral nerve stimulation (PNS) therapy for the treatment of pain following total knee arthroplasty (TKA) utilizing preoperative lead placement
Investigational (Test) Device	SPRINT® Beta Peripheral Nerve Stimulation (PNS) System [REDACTED]
Study Design	Prospective, Comparative Effectiveness Randomized Controlled Trial
Primary Study Objective	To determine if the addition of PNS therapy to the site's standard of care for treatment of knee pain following TKA is significantly different than that of the site's standard of care alone.
Study Plan	
Individuals undergoing a primary unilateral TKA will be considered for enrollment into the study. After obtaining informed consent, potential subjects will be evaluated for general eligibility.
 
Qualifying subjects will be randomized to either Group #1 (Treatment) or Group #2 (Control). All subjects will receive the site's standard of care (SOC) for the treatment of knee pain before, during, and after the TKA. Subjects assigned to Group #1 will also receive Peripheral Nerve Stimulation Therapy for up to approximately 30 days before the procedure, and again starting immediately after the TKA for a total of up to 60 days.
 
[REDACTED]
 
[REDACTED]
 
Subjects will receive treatment [REDACTED] for 4 weeks post-TKA. At the conclusion of the treatment period, the leads will be removed.
 
Subjects in both groups will receive the site's SOC for treatment of knee pain before, during and after TKA. Subjects will complete a daily diary recording their medication usage and daily [REDACTED] Pain [REDACTED]. Other outcomes that will be assessed include tests of function, stimulation characteristics, surveys/questionnaires, pain scores and pain treatments.
 
Outcomes will be assessed based on the schedule of study procedures (Appendix A).

Sites (N)	Up to 10 investigational sites
Subjects (N)	Approximately 50 subjects will be enrolled. Subjects will be randomized to either Group #1 (Treatment) or Group #2 (Control).
Inclusion Criteria	
 • Between the age of 21 and 90 years old • Scheduled to undergo a primary unilateral total knee replacement procedure • Able to understand and provide written consent • Able to comply with all study requirements (e.g., if needed, has a caregiver to assist)

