7.2 Number of Subjects

Up to 50 subjects will be enrolled in this study. All subjects will receive the site's SOC for the treatment of knee pain before, during and following TKA. Subjects assigned to Group #1 will also receive PNS Therapy before and after TKA. All subjects who sign an informed consent form will receive a subject ID number. Qualifying subjects will be randomized to either Group #1 (Treatment) or Group #2 (Control).

[REDACTED]

[REDACTED]

[REDACTED]

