8.6 Study Visit Windows

The acceptable windows for each encounter are listed below in **Table 1**.

Table 1 Study Visit Windows

Visit Number	Visit Name	Window
1	Consent and Randomization Visit	[REDACTED]
2	Lead Placement Visit ^T and Check-in Call	[REDACTED]
3	Day of TKA (POD 0) Visit	[REDACTED]
4a, b, c...	Daily in-hospital Visits	[REDACTED]
5	1 week post-TKA Call	[REDACTED]
6	2 weeks post-TKA Visit	[REDACTED]
7	3 weeks post-TKA Call	[REDACTED]
8	4 weeks post-TKA Visit (EOT ^T)	[REDACTED]
9	2 months post-TKA Call	[REDACTED]
10	3 months post-TKA Call	[REDACTED]
11	12 months post-TKA Call	[REDACTED]

^T Treatment Group (Group #1) Only

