10.1 Analysis of Outcomes and Exploratory Measures

A table of outcomes and exploratory measures to be collected during the study can be found in Appendix A.

“Average Pain” [REDACTED] will be measured daily in both groups for 7 days prior to Visit 2, for 7 days prior to the TKA, and for the first 4 weeks post-TKA. [REDACTED]

[REDACTED] An overall mean across all subjects for the first 4 weeks following TKA surgery will be calculated [REDACTED]. The average [REDACTED] score over the 4 weeks will be compared between Groups. [REDACTED]

[REDACTED]

At several visits, subjects will be asked to report their weekly "Average Pain" [REDACTED]. The mean [REDACTED] will be calculated and compared between the Groups.

Pain treatments and analgesic usage will be recorded. Changes in opioid usage may be calculated using morphine equivalent dosing (MED). [REDACTED]

[REDACTED] subjects taking opioids [REDACTED] will be queried for side effects associated with opioids. [REDACTED] These pain treatment and analgesic-related outcomes will be compared between the Groups.

Functional tests performed during the study will include the Timed Up and Go [REDACTED] and the Six-Minute Walk Test. The data from these tests will be analyzed [REDACTED]

[REDACTED]

Surveys performed during the study will include the [REDACTED] Patient Global Impression of Change (PGIC), time to meet recovery milestones, Inpatient Pain Management Experience Survey, Subject Satisfaction Survey, and Clinician Satisfaction Survey. [REDACTED]

Subjects will be asked to report the number of Physical Therapy Sessions they attended each week post-TKA. [REDACTED]

Throughout the study, subjects will answer questions to describe their pain distribution and stimulation-evoked comfortable sensation (Group #1 only) coverage. [REDACTED]

The number of hours of stimulation delivered (Group #1 only) as measured by the stimulator will be recorded throughout the study. [REDACTED]

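### Does a first diary week that may be completed after allocation is known undermine the pain comparison?

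*Combined protocol and SAP*

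**What the plan says.** Table 1 in section 8.6 calls Visit 1 the "Consent and Randomization Visit", and section 8.5.1 carries the same title. Under it, "all inclusion/exclusion criteria will be verified by completing the eligibility form and then all baseline information and outcome measurements will be collected", on the case report form. The diary comes in a separate sentence: "Subjects will receive a one-week daily diary to be completed prior to Visit 2". Section 7.2 adds "Qualifying subjects will be randomized to either Group #1 (Treatment) or Group #2 (Control", without placing that step relative to the baseline measurements or the diary.

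Section 8.5.2 describes Visit 2 as "Lead Placement Visit (Group #1 only) and Check-in Call (Both Groups". The synopsis (section 2.0) states "Subjects assigned to Group #1 will also receive Peripheral Nerve Stimulation Therapy for up to approximately 30 days before the procedure". Section 10.1 says average pain "will be measured daily in both groups for 7 days prior to Visit 2, for 7 days prior to the TKA", and for the first four weeks after surgery.

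Section 5.2 defines the primary outcome as daily walking pain averaged over those four weeks. Section 10.1 says the average "score over the 4 weeks will be compared between Groups". No baseline term is visible there, although the neighbouring text is redacted.

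**The concern.** Pain is self-reported and the visible text describes no sham or blinding of subjects. Someone who has just learned that they will, or will not, receive stimulation may rate pain differently in the following week. The later pre-operative week offers no alternative, because it can fall within the period of pre-operative stimulation in Group #1. An analyst looking for a diary baseline before treatment would therefore turn to the first week.

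If the diary means differed between groups because of reporting, adjusting for them or subtracting them would carry that difference into the estimated effect. At stake are any baseline-adjusted or change-from-baseline analyses of diary pain, and possibly of opioid use, since section 5.3 records analgesic use before surgery in a diary.

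**Working it through.** **Order of events.** Reading sections 8.5.1, 8.5.2, 10.1 and 2.0 together gives:

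1. Visit 1: consent, eligibility and baseline measurements; randomization by title only.
2. First diary week, 7 days.
3. Visit 2: lead placement in Group #1. Subjects in that group know their allocation by now.
4. Stimulation in Group #1 for up to about 30 days, which can include the 7-day diary before surgery.
5. Surgery, then the four-week diary that supplies the primary outcome.

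Only step 2 is a diary week clearly before stimulation. That it follows allocation rests on the visit title; the body of section 8.5.1 does not describe the randomization step or say when the result is disclosed.

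**Which visible analyses use step 2?**

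- Primary comparison (5.2, 10.1): step 5 only.
- Opioid use (10.1): a change may be calculated, but it is optional and its reference period is not visible. Cumulative analgesic use is already a listed outcome.
- Change in pain, function and stiffness (2.0): section 5.3 describes a 24-item questionnaire covering these three domains, not the diary.
- Baseline information (8.5.1): attached to Visit 1 measurements, not to the diary.

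No visible analysis is tied to the first diary.

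**Size if it were used.** The documents give no inputs, so these are assumptions. Let known allocation shift Group #1 reporting by b at baseline and p after surgery, in SD units with equal SDs; let r be the correlation between baseline and outcome, and let there be no treatment effect. The expected bias is:

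- post-surgery means: p
- baseline-adjusted (ANCOVA): p - r*b, the outcome shift less slope times baseline shift
- change scores: p - b

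With b = 0.25 and r = 0.2 to 0.6, r*b runs from 0.2*0.25 = 0.05 to 0.6*0.25 = 0.15:

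| p | Post means | ANCOVA | Change |
|---|---|---|---|
| 0 | 0 | -0.05 to -0.15 | -0.25 |
| 0.125 | +0.125 | +0.075 to -0.025 | -0.125 |
| 0.25 | +0.25 | +0.20 to +0.10 | 0 |
| -0.125 | -0.125 | -0.175 to -0.275 | -0.375 |

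The post-means column does not contain b, so the diary cannot bias the visible primary comparison in any row. Taking the diary before disclosure sets b = 0, and all three analyses then carry p. The primary comparison is the same under either order. For the other two the new order is not always better: with p = b = 0.25, change scores go from a bias of 0 to 0.25.

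**The case for a change.** The case for acting is reasonable. The visit title appears in two places, so it is not a stray heading. Section 8.3.2 applies two exclusions (bleeding or INR, and pregnancy) to Group #1 only, while section 8.5.1 verifies all criteria at Visit 1; this suggests that allocation may be known that early. Group #1 subjects may repeat Visit 2, and section 10.1 does not say which Visit 2 anchors the diary week. A confirming sentence would cost almost nothing, and the synopsis shows that some change outcomes are planned.

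The order of events stands as an open question. The rest does not carry a change:

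- The group-specific exclusions also weaken the obvious alternative. If allocation is known when eligibility is checked, a Visit 1 rating may follow allocation too. It is not proof either way, since those checks could be completed later.
- The diary is handed out under Visit 1, so the natural reading is the week before the first Visit 2.
- Redacted text follows the randomization sentence in 7.2, opens the Visit 2 description and surrounds the comparison in 10.1. The visit windows are redacted, and Appendix A is not in the available text. Disclosure timing and the baseline definition could sit in any of these places, so their absence cannot be held against the plan.
- Moving allocation about a week later would need an added contact and provisional booking of lead-placement slots, and would leave any post-surgery reporting shift untouched.

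**Conclusion.** The concern does not call for a change. The first diary week may well be completed with allocation known, but harm would need four further things that are not shown: disclosure before or during that week, different reporting by group, use of the diary as covariate or change reference, and no measure recorded before disclosure. The diary's contribution to bias in the visible primary comparison is 0 for every assumed b. The 0.05 to 0.15 SD (adjusted) and 0.25 SD (change score) figures hold only for an assumed 0.25 SD shift confined to the diary, in analyses the visible text does not specify.

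This is a gap that analysts can fill sensibly: compare post-surgery means as written and, for any adjusted or change analysis, prefer a measure recorded before disclosure and say which one was used. The conclusion rests on the unredacted text. It would need another look if a redacted part made the first diary the baseline for a main analysis.

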5.2 Primary Outcome

The primary outcome of this study will be the average daily pain while walking over the first 4 weeks following TKA surgery.

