8.8 Early Termination

8.9 *Subject Compensation*

Subjects will receive [REDACTED] compensation for taking part in all study visits. Compensation will be based on the subject completing milestones within the study. The disbursement schedule will be as follows:

- [REDACTED] after the completion of Visit 1
- [REDACTED] after the completion of Visit 2
- [REDACTED] after the completion of each Visit 3, 4 (only one instance), 6, and 8
- [REDACTED] after the completion of each Visit 5, 7, 9 10, and 11

If a subject in Group #1 volunteers to participate in an additional Visit 2 (returns for another session of stimulation testing or for a lead replacement), the subject will receive an [REDACTED] compensation at the completion of that visit. All requirements for Visit 2 will be repeated.

[REDACTED]

9.0 *Data Management*

9.1 *Subject Screening and Identification Log*

A subject screening log will be completed at the investigational site for all subjects who were considered for the study. Those individuals who are excluded will be listed along with the reason for exclusion.

[REDACTED]

The Subject Identification log will be completed for subjects enrolled in the study.

9.2 *Data Collection*

Case Report Forms (CRFs) will be completed for each subject who signs an informed consent form up until the point of discharge from the study. CRFs will be completed and maintained in a fashion that is consistent with accepted Good Clinical Practices. All paper documents will be completed in permanent blue or black ink and all entries will be made in a legible fashion. If necessary, corrections will be made by using a single line strikeout with the initials and date of the person making the correction. The corrections will be made so as not to obscure the original data. Correction fluid or correction tape may not be used. All paper study documentation will be stored in a locked storage facility (either a locked office or a locked cabinet).

9.3 *Subject Numbering*

All subjects who sign an informed consent will be given a unique alpha - numerical Subject ID number.

[REDACTED]

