10.2 Plan to maximize subject retention and minimize loss of data

Significant efforts will be made to maintain maximum subject retention and follow up data and minimize the percentage of missing data.

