10.4 Per Protocol and Intent to Treat Analyses

Analyses of the primary and secondary effectiveness endpoints will be conducted on the intent-to-treat (ITT) population and the per-protocol (PP) population at each specified study interval defined as follows:

PP Population: [REDACTED]

ITT Population: [REDACTED]

[REDACTED]

[REDACTED]

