12.0 Adverse Events and Unanticipated Adverse Device Effects

Adverse events (AEs) that occur during the study will be captured on CRFs. Specific details regarding any observed AE will be collected on a separate Adverse Event Form. The severity of each Adverse Event will be collected as well as its relationship to the System. AEs will be classified as mild (event that causes mild discomfort or inconvenience and resolves without treatment), moderate (event that requires medical intervention or medication to treat), or severe (event that requires intervention to prevent permanent impairment or damage, an event that requires or prolongs hospitalization, or an event that is disabling, causing permanent damage, life threatening, or causing death). Adverse events will also be classified as serious or non-serious. Any necessary treatment or intervention required and the resolution status of the adverse event will also be documented. Adverse Events will be followed to resolution. Side effects from narcotic therapy will be collected but not reported as adverse events. Common symptoms after TKA surgery related to the normal healing process (i.e., swelling, bruising, stiffness, incision tenderness, drainage, etc.) will also not be reported as adverse events unless they meet the definition and criteria for AE reporting

An Adverse Device Effect (ADE) is a device-related Adverse Event. All ADE's are further categorized as anticipated or unanticipated. Any ADE's specified in the Risk Analysis of this Investigational Plan will be considered "anticipated". All other ADE's are considered "unanticipated". Anticipated events that occur with a greater frequency than expected are also considered unanticipated.

An Unanticipated Adverse Device Effect (UADE) is defined as any serious adverse effect on health or safety or any life threatening problem or death caused by, or associated with, a device, if that effect, problem or death was not previously identified in nature, severity or degree of incidence in this Investigational Plan or application or any other unanticipated serious problem associated with a device that relates to the rights, safety or welfare of subjects.

Table 2 Unanticipated Adverse Device Event Sponsor Contact Information

UNANTICIPATED ADVERSE DEVICE EVENT SPONSOR CONTACT INFORMATION			
Name/Title	Email address	Telephone Number	Fax Number
[REDACTED]	[REDACTED]	[REDACTED]	[REDACTED]
[REDACTED]	[REDACTED]	[REDACTED]	[REDACTED]

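### Option c of section 8.5.2 removes some Group #1 subjects from the study after randomisation and before the primary outcome window, with no visible provision to collect their post-TKA pain or later adverse events

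*Combined protocol and SAP*

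**What the plan says.** Section 8.5.1 and Table 1 (section 8.6) place randomisation at Visit 1. Lead placement is at Visit 2, for Group #1 only, before the day of TKA at Visit 3.

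Section 8.5.2 gives three outcomes for Group #1 at the end of the lead placement visit:

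- **Option a:** go on to treatment.
- **Option b:** for unfinished placement or testing, or no response to stimulation, "the investigator may present the subject with the option to return for a repeat lead placement visit".
- **Option c:** terminate from the study. The trigger is "If the subject does not wish to continue with further lead placement or if an additional lead placement visit is needed", followed by a redacted qualifier. The consequence is that "they will be terminated from the study if no adverse events (AE) are noted at the 24-48 hour telephone Check-In Call". A subject with an adverse event at that call is followed until it resolves.

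Four other places bear on what happens next:

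- Section 5.2 defines the primary outcome as "average daily pain while walking over the first 4 weeks following TKA surgery".
- Section 9.2 says that case report forms "will be completed for each subject who signs an informed consent form up until the point of discharge from the study".
- Section 12.0 says "Adverse events (AEs) that occur during the study will be captured on CRFs".
- Section 10.2 promises that "Significant efforts will be made to maintain maximum subject retention and follow up data and minimize the percentage of missing data", and section 10.4 that "Analyses of the primary and secondary effectiveness endpoints will be conducted on the intent-to-treat (ITT) population and the per-protocol (PP) population".

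The ITT and PP definitions, the body of section 8.8 (Early Termination), most of Visit 2 and Appendix A cannot be read.

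**The concern.** Option c ends study participation, where ending stimulation would have been enough. It acts after randomisation, in one arm, and before any of the primary outcome is observed. The reasons for exit are not random: they concern how placement went, whether the subject responded to stimulation (undefined in the visible text, and not shown to mean pain relief) and willingness to repeat the procedure.

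The stated objective is the effect of adding PNS to standard of care. Failed or refused placement is part of adding PNS. If these subjects have no post-TKA data, an analysis of observed data compares Group #1 subjects whose placement was accepted with all of Control, which answers a different question.

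There is a safety side as well. Because case report forms run only to discharge from the study and adverse events are captured on those forms, a device- or protocol-related event that first appears after a clean 24-48 hour call has no visible route into the safety endpoint.

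**Working it through.** **Sequence in the visible text.** Randomise (Visit 1) → lead placement, Group #1 only (Visit 2) → option c exit after a clean 24-48 hour call → TKA (Visit 3) → four weeks of walking-pain diary. The exit comes before the whole outcome window. Reading termination as discharge in the sense of section 9.2, data collection stops there.

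**No figure to reproduce.** The plan gives no visible placement failure rate, SD, pain scale, effect size or allocation ratio. Section 7.2 gives only up to 50 subjects. What follows is illustration and assumes 25 per arm and a 0-10 scale.

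**Notation.**
- k = number of exits, and f = k/25.
- D = effect of PNS in subjects who receive it (negative = benefit).
- g = mean pain that terminated subjects would have under standard of care, minus the same for retained subjects (positive = worse prognosis).
- μ = mean under standard of care in everyone. Retained subjects then average μ − f·g, and terminated subjects μ + (1−f)·g.

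**Formulas.** Terminated subjects, if followed, would receive standard of care only.
- As-randomised effect = (1−f)(μ − f·g + D) + f(μ + (1−f)·g) − μ = (1−f)·D
- Observed-data effect = D − f·g
- Bias = observed − as-randomised = f·(D − g)

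**(1) D = −1.5, g = 0.** The observed-data benefit is 1.50 throughout.

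| k | f | As-randomised benefit | Overstatement | Relative, 1/(1−f) − 1 |
|---|---|---|---|---|
| 0 | 0 | 1.50 | 0 | 0% |
| 1 | 0.04 | 1.44 | 0.06 | 4.2% |
| 2 | 0.08 | 1.38 | 0.12 | 8.7% |
| 3 | 0.12 | 1.32 | 0.18 | 13.6% |
| 4 | 0.16 | 1.26 | 0.24 | 19.0% |
| 5 | 0.20 | 1.20 | 0.30 | 25.0% |

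If allocation were 33:17, f = k/33 and the overstatement for 1 to 5 exits is 0.05 to 0.23.

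**(2) D = −1.5, k = 5, unequal prognosis.**
- g = +1: 0.2 × (−2.5) = −0.50, toward PNS
- g = −1: 0.2 × (−0.5) = −0.10, toward PNS
- g = −2: 0.2 × (+0.5) = +0.10, against PNS

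The sign changes at g = D, that is, when terminated subjects would do more than 1.5 points better.

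**(3) No true effect (D = 0), SD 2.** Bias = −f·g and SE = 2·√(1/(25−k) + 1/25). For k = 5, g = +1 the bias is −0.20 and the SE 0.60. The table gives the share of trials with two-sided p < 0.05 in favour of PNS (nominal 2.5%), from simulation of 200,000 trials per cell.

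| k | g = −1 | g = 0 | g = +1 |
|---|---|---|---|
| 1 | 2.1% | 2.5% | 2.9% |
| 3 | 1.6% | 2.5% | 3.9% |
| 5 | 1.1% | 2.5% | 5.0% |

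For k = 5, g = +1 the figure is 6.1% with SD 1.5 and 4.5% with SD 2.5. A noncentral t calculation with noncentrality f·g/SE agrees within about 0.3 percentage points.

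**(4) No assumption on SD or prognosis.** Each missing value could lie anywhere from 0 to 10, so the Group #1 mean is undetermined by 10·k/25 = 0.4·k points: 0.4 for one exit and 2.0 for five.

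**The case against.** The strongest objection is that every place where follow-up of these subjects might be written is unreadable: section 8.8, most of Visit 2, the ITT and PP definitions and Appendix A. Redacted text is not missing from the plan, and no visible text says that an observed-data analysis will be used. This stands to the extent that the point must be limited to what is visible. It does not remove the point. The visible sentence says affirmatively that these subjects leave the study. A redacted ITT definition could say how they are counted but could not supply diaries that were never kept. If section 8.8 does keep them in follow-up, it contradicts option c and the two must be reconciled.

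Materiality is also open to challenge. One exit moves the estimate by 0.06 points and the false-benefit rate from 2.5% to 2.9%. Five of 25 is an assumed rate, option b should reduce exits, and the direction is not determined. All of this is correct, and it limits the severity.

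On estimand, with equal prognosis 1.50 is the right effect in subjects who received PNS. That is true, but the stated objective concerns adding PNS to standard of care, which is the as-randomised effect.

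On safety, an adverse event noted at the call is followed to resolution, and section 8.5.10 allows unscheduled visits for adverse events, though it is not clear that these reach terminated subjects. Only events arising after a clean call are in question.

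**Conclusion.** The concern holds as a point that should be fixed. By a stated rule, option c creates missing primary outcome data in one arm after randomisation, which works against the retention aim in section 10.2 and the ITT analysis in section 10.4. The mechanism is clear from the visible text, but its frequency is not, so confidence is medium.

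On the assumptions above, the bias is zero with no exits. If PNS works and prognosis is similar, the benefit is overstated by a few hundredths to a few tenths of a point. If PNS does nothing, bias arises only where terminated subjects differ in prognosis, and it can go either way. With at most 50 subjects, a handful of one-sided losses is enough to matter to interpretation.

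**What to change.** Amend option c so that stopping device procedures and leaving the study are separate events:

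- Subjects who exit at lead placement and still consent to follow-up keep the same post-TKA diary, visits or calls and adverse event collection as other subjects.
- They are analysed in Group #1 in the ITT analysis.
- For outcomes still missing, prespecify a sensitivity analysis. One example is a tipping-point analysis that shifts the missing Group #1 outcomes from 2 points better to 2 points worse than standard of care. The range is for the sponsor to justify.
- Report the number of option c exits by reason.
- Reconcile the wording with section 8.8 and the ITT definition, and state whether the section 8.4 restrictions continue for these subjects. Other grounds for termination can stay as they are.

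The cost is about a paragraph of amendment, possible small edits to the schedule, case report forms and consent, and diaries and calls for a few subjects already enrolled. The estimated effect may be somewhat smaller. Some subjects will decline follow-up, which is why the sensitivity analysis is still needed. The change has to be made in the protocol, because diaries that were never collected cannot be recovered at analysis.
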